7. INSTITUTIONAL REVIEW BOARD AND INFORMED CONSENT

Institutional Review Board (IRB) review and approval of the study protocol and Informed Consent Form will be obtained prior to initiation of the study. Amendments to the study protocol and consent form generated during the course of the study will also require IRB approval.

8. MANAGEMENT OF INTERCURRENT EVENTS

8.1. Modification of Protocol

Neither an Investigator nor Braintree Laboratories will modify the protocol without first obtaining the concurrence of the other and the IRB. Investigators that continually violate the protocol or commit a serious violation may be subject to termination from the study. The study may be halted if at any time an Investigator or Braintree Laboratories deems the incidence or severity of adverse events to be unacceptable.

8.2. Subjects Discontinued from the Study

Subjects may be dropped from the study for any of the following reasons:

- 1) Subject did not meet BM Entry Criteria.
- 2) Subject did not meet Diary Compliance Criterion.
- 3) Subject took prohibited laxatives during the Screening or Treatment Period
- 4) An adverse event requiring discontinuation (including failure to tolerate study medication).
- 5) The Investigator decides that the subject should be dropped from the study (e.g. serious adverse event, protocol violation, non-compliance).
- The subject decides to withdraw from the study. Subjects are free to withdraw their consent and discontinue participation in the study at any time.

Braintree Laboratories should be contacted if possible prior to discontinuation of any subject. If a subject is discontinued from the study, Braintree Laboratories must be notified with an explanation for all discontinuances.

9. DATA ANALYSIS

9.1. Sample Size

Six hundred subjects will be randomly assigned to BLI400 (21 g/day dose) or placebo in a ratio of 1:1 (300 BLI400, 300 placebo). The definition of a weekly responder is based on weekly assessments of complete spontaneous bowel movements (CSBMs).

Based on data from a previous laxative study (Lembo et al, 2011) utilizing this primary efficacy variable (percent of subjects who are responders), it is anticipated that approximately 20% of subjects would be classified as responders in the BLI400 arm, with a placebo response up to 10%. The proposed study size will have approximately 90% power to detect a difference of 10% between the active and placebo groups at a two-sided significance level of 0.05.

9.2. Null and Alternative Hypotheses

The primary objective of this study is to compare the safety and efficacy BLI400 Laxative to placebo in subjects with constipation. To establish this, the primary comparison of interest will be on the overall responder percentage based on 12 weeks of treatment. A weekly responder is a subject who has \geq 3 CSBMs and an increase from baseline of > 1 CSBM in that week.

The null hypothesis will be that there is no difference in the response rates between BLI400 Laxative and placebo; the alternative hypothesis is that the response rate is higher for BLI400 laxative than for placebo.

9.3. Planned Analyses

Data analysis will be performed after all subjects have completed the study. No interim analyses are planned.

9.3.1. Demographic and Baseline Characteristics

An analysis of baseline comparability of the following demographic and baseline characteristics for the treatment groups will be performed.

- Age (ANOVA)
- Gender (CMH Chi square)

- Race/ethnicity (CMH Chi square)
- Weight (ANOVA)
- Screening Period Constipation Status (ANOVA)

9.3.2. Efficacy Analyses

Primary Efficacy Endpoint

The primary efficacy endpoint will be assessed on the basis of a binary outcome of overall treatment success or failure. The primary efficacy endpoint will be the proportion of subjects who are weekly responders for 9 out of the first 12 weeks of treatment, with at least 3 of these weeks occurring during weeks 9–12 of treatment. A weekly responder is a subject who has \geq 3 CSBMs and an increase from baseline of > 1 CSBM in that week. A CSBM is a bowel movement that occurs with no rescue laxative use in the previous 24 hours and that is accompanied by a sense of complete evacuation.

The following equation will be used to calculate the weekly CSBM frequency:

CSBM frequency = $7 \times (Number of CSBMs/number of days with non-missing CSBM assessments)$

If a subject has fewer than four days of data observed for a week, then that subject's data should be considered missing for that entire week and the subject considered a non-responder.

The primary efficacy endpoint will be analyzed using the CMH test controlling for the effect of study center. The presence of a treatment-by-center interaction will be investigated by the Breslow-Day test of homogeneity of the odds ratio. The strategy for pooling centers will be based on geographical considerations, with low enrolling centers pooled by geographic region. Details of any pooling performed will be documented prior to database lock and unblinding of the study.

No bowel movements that occur within 24 hours of a rescue bisacodyl (or other prohibited laxative) dose will be included in primary or secondary efficacy analyses.

Secondary Endpoints

Secondary endpoints will include the following:

- Overall response by gender and age group (< $65, \ge 65$ years, ≥ 75 years)
- Number of study medication doses taken per week
- Number of rescue doses taken per week (includes bisacodyl and other non-study laxative)
- % of subjects not meeting ROME criteria at the end of each treatment week
- BM Frequency per week (SBM and CSBM)
- BM Frequency per month (SBM and CSBM)
- BM Symptom Ratings per week (straining, consistency, urgency, Bristol score)
- BM Symptom Ratings per month (straining, consistency, urgency, Bristol score)
- Number of diarrhea episodes per week (diarrhea is defined as > 3 watery stools per day)

9.3.3.Safety Analyses

Analysis of safety will be performed using the modified Intent-to-Treat population (see Section 9.4). Safety analyses may also be presented by age, gender and racial subgroup.

Adverse Events

Adverse Events will be coded using the MedDRA classification to provide a preferred term and primary system organ class for each event. Proportions of subjects with adverse events will be presented by treatment group. Tables of AEs will be presented by system organ class and preferred term, and include overall totals for AEs within each system organ class. Counting will be done by subject and not by event. A table of counts and percentages will also be made of those subjects with SAEs or AEs which led to withdrawal from the study.

Treatment-emergent AEs are defined as adverse events that had an onset day and time on or after the day and time of the first dose of study drug up to 14 days after the last dose of

study medication. Adverse Events having missing onset dates will be considered as treatment-emergent.

The difference in adverse event rates between study groups will be tested by Chi-Square or Fisher's exact test with 95% confidence intervals. Adverse events will be presented for the overall Treatment Period.

Laboratory Parameters

Summary statistics (i.e., mean, minimum, maximum, standard deviation, and number of subjects) will be presented for each treatment group for each laboratory parameter at each visit. When calculating the summary statistics only, the last observation within a visit window will be used if there are multiple observations. Changes from Visit 1 (Screening) will be presented in a similar format. An additional listing will be provided of those subjects who have clinically significant laboratory values. The data will also be presented as shift tables, and clinically significant abnormalities will be examined.

Results of laboratory tests for the change from Visit 1 (Screening) and group differences will be tested using ANOVA.

Vital Signs

Summary statistics (i.e., mean, minimum, maximum, standard deviation, and number of subjects) will be presented for each treatment group for each vital sign at each visit. When calculating the summary statistics only, the last observation within a visit window will be used if there are multiple observations. The data will also be presented as shift tables and clinically significant abnormalities will be examined.

ECG variables will be tabulated and presented for data collected at each visit. Data will be tabulated and summarized with descriptive statistics (N, mean, SD, CV%, SEM, minimum, and maximum) for each of the ECG variables. The differences in ECG variables between Visit 1 (Screening) and Visit 8 will be tested using ANOVA.

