	4.2. Modified Intention-to-Treat (mITT) Population	
9.	4.3. Per-Protocol Population	31
10.	DRUG INVENTORY AND DISPOSITION	
11.	STUDY MONITORING	
12.	DOCUMENTS AND NOTIFICATIONS	
12.1	. INFORMED CONSENT	
12.2	. Institutional Review Board	
12.3	. Amendments to the Protocol	
12.4	. DATA RECORDS	
13.	PUBLICATION AND AGREEMENT	
14.	INVESTIGATORS AGREEMENT	
15.	REFERENCES	

CLINICAL PROTOCOL SUMMARY SHEET

STUDY TITLE:	A Safety and Efficacy Evaluation of BLI400 Laxative in Constipated Adults
PROTOCOL:	BLI400-302
VERSION DATE:	9-15-2016
IND NUMBER:	118,906

OBJECTIVE:

To evaluate a daily dose of BLI400 Laxative for safety and efficacy versus placebo in constipated adults.

STUDY DESIGN:

This will be a randomized, double-blind, parallel, multi-center study.

SUBJECTS:

Approximately 600 male or female constipated adult subjects will be randomized in this study after completing a 14 day screening period to confirm constipation status.

Approximately 30% of enrolled subjects will be elderly (greater than 65 years of age at time of randomization)

STUDY MEDICATIONS:

- Group 1: BLI400 Laxative (21 grams of Lactitol Monohydrate, NF)
- Group 2: Placebo (regular maltodextrin)

DURATION OF TREATMENT

Subjects will take BLI400 laxative or placebo daily for 6 months. Participation in this study will last for approximately 7 months, including the 14 day Screening Period.

PRIMARY ENDPOINT

The primary endpoint is the proportion of subjects who are weekly responders for at least 9 out of the first 12 weeks, with at least 3 of these weeks occurring during weeks 9-12. A weekly responder is a subject who has ≥ 3 complete spontaneous bowel movements (CSBMs) per week and an increase from baseline of > 1 CSBM in that week.

SECONDARY ENDPOINTS

Secondary endpoints will include but are not limited to the following:

- Weekly SBM and CSBM frequency rates during weeks 1 12
- Weekly stool and symptom ratings (stool consistency, stool straining, abdominal bloating, abdominal discomfort) during weeks 1 12
- Weekly SBM and CSBM frequency rates after week 12
- Weekly stool and symptom ratings (stool consistency, stool straining, abdominal bloating, abdominal discomfort) after week 12

Safety will be assessed using treatment emergent adverse event, laboratory, and ECG data.

Confidential

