4.1.3. Electronic Subject Diary during Screening Period

Subjects will be asked to use an electronic subject diary to self-report their bowel movement and rescue medication experiences each day. Subjects will be required to enter data on each bowel movement as soon as possible following completion. This data will include assessments of BM completeness, consistency, straining and urgency.

Each dosing episode of rescue medication will be entered. Instructions on how to complete the diary questions will be supplied in a separate manual.

4.2. Visit 2

Subjects will return to the study center as soon as possible after the 14 day Screening Period for Visit 2.

BM Entry Criteria – to be eligible for randomization, subjects must meet the following criteria related to their Screening Period BMs:

- average of fewer than 3 complete spontaneous bowel movements (CSBMs) per week during the 14 day Screening Period. A CSBM is defined as a bowel movement which has occurred with no rescue laxative use in the prior 24 hours and is accompanied by a sense of complete evacuation
- average of fewer than 6 spontaneous bowel movements (SBMs) per week during the 14 day Screening Period. An SBM is defined as a bowel movement which has occurred with no rescue laxative use in the prior 24 hours
- No more than 1 SBM with a Bristol Stool rating of 6
- No SBMs with a Bristol Stool rating of 7

Diary Compliance Criterion to be eligible for randomization, a subject must have completed an average of at least one Bowel Movement Diary entry per day for 5 or more days per week during the 14 day Screening Period

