4.3. Treatment Period

4.3.1. Electronic Subject Diary during Treatment Period

Each day during the Treatment Period, subjects will complete their e-diary reporting. Subjects will report each bowel movement as it occurs along with related symptoms and characteristics (consistency, straining, urgency, completeness). Subjects will also report their daily study medication and rescue medication doses (if applicable) as they occur.

4.3.2. Treatment Day 1

Starting the morning of Treatment Day 1 (the day after randomization), subjects will measure two (2) capfuls of study medication and ingest it mixed in a beverage of their choice. When possible, subjects should take each dose at appromiately the same time every day (preferably in the morning). Subjects that develop persistent diarrhea or loose stools should contact their study center. Subjects with persistent diarrhea or loose stools will be allowed to adjust their dose down to 10.5g (1 capful) per day.

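### Do days without a bowel movement drop out of the weekly CSBM rate and so misclassify responders?

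*Combined protocol and SAP*

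**What the plan says.** Section 9.3.2 defines the weekly CSBM frequency as 7 times the number of CSBMs divided by the "number of days with non-missing CSBM assessments". The next rule handles sparse weeks: "If a subject has fewer than four days of data observed for a week, then that subject's data should be considered missing", and the subject is then a non-responder for that week. A weekly responder needs at least 3 CSBMs and "an increase from baseline of > 1 CSBM in that week". An overall responder needs 9 such weeks of the first 12, at least 3 of them in weeks 9–12.

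The diary is described in two places. Section 4.1.3 (screening) asks for daily self-report and says "Subjects will be required to enter data on each bowel movement as soon as possible following completion". Section 4.3.1 (treatment) requires the e-diary to be completed each day, says "Subjects will report each bowel movement as it occurs", and adds study drug and rescue doses. Section 4.1.3 leaves the instructions for the diary questions to a separate manual. The Diary Compliance Criterion in Section 4.2, which covers the 14 days of screening, says that "a subject must have completed an average of at least one Bowel Movement Diary entry per day for 5 or more days per week".

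**The concern.** Completeness is a property of a bowel movement, and both diary sections describe records made movement by movement. Neither mentions an entry confirming that there was no movement that day. Taken literally, a day without a movement has no CSBM assessment. It would then leave the denominator and might not count toward the four days. In constipated subjects those days are true zeros. Days whose only movement is disregarded because of rescue bisacodyl raise the same question.

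The weekly responder status behind the primary endpoint would then be wrong in both directions, and baseline would be inflated if computed the same way. Section 9.3.2 also uses one phrase for the denominator and another for the four-day rule, so two programmers could count different days.

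**Working it through.** **Planning figure.** Section 9.1 assumes 20% versus 10% responders, 300 per arm, two-sided 0.05, and states about 90% power. The pooled rate is 0.15. The standard error under the null is √(2 × 0.15 × 0.85/300) = 0.02915; under the alternative it is √((0.16 + 0.09)/300) = 0.02887. Power = Φ((0.10 − 1.96 × 0.02915)/0.02887) = Φ(1.48) = 93%. The stated figure stands and does not depend on how a day is counted.

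**Two readings of one week.** Let C be the CSBM count and k the number of days with a recorded movement, in a week where the diary was completed on all 7 days.

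- *Diary-day reading:* days without a movement are zeros, so frequency = 7 × C/7 = C.
- *Movement-day reading:* frequency = 7 × C/k, and the week is missing if k < 4.

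With baseline 0, enumerating k from 1 to 7 and C from 0 to 5 gives disagreement only here:

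| k | C | Movement-day | Diary-day |
|---|---|---|---|
| 4 | 2 | 7 × 2/4 = 3.5, passes 3 | 2.0, fails |
| 1 to 3 | 3 or more | missing, non-response | 3.0 or more, passes |

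At k = 5 and C = 2 the value is 7 × 2/5 = 2.8, which does not cross 3.

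**Baseline.** Suppose 3 CSBMs in 14 screening days, with movements on 10 of them. The movement-day rate is 7 × 3/10 = 2.1; the diary-day rate is 7 × 3/14 = 1.5. A treatment week with 3 CSBMs and movements on all 7 days changes by 3.0 − 2.1 = 0.9 (fails the requirement of more than 1) or by 3.0 − 1.5 = 1.5 (passes).

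**How often, if the movement-day reading held.** Assume Poisson movements at a weekly rate λ, so a day has at least one with probability p = 1 − exp(−λ/7). The chance that a fully reported week has fewer than 4 such days is P(Binomial(7, p) ≤ 3): 64% at λ = 4 (p = 0.435), 48% at λ = 5 (p = 0.511) and 34% at λ = 6 (p = 0.576).

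**Is that reading compatible with the protocol?** The compliance criterion amounts to 5 × 2 = 10 of the 14 screening days. Under movement-only entry the chance of meeting it is P(Binomial(14, p) ≥ 10). At λ = 3 (p = 0.349) this is 0.6%; at λ = 6 it is 22%. Section 3.5.1 admits subjects with a history of fewer than 3 spontaneous defecations a week, and Section 4.2 caps screening at fewer than 6 spontaneous movements a week. Movements after rescue would add some entries, but randomizing about 600 such subjects is hard to reconcile with movement-only entry. The criterion is workable if a diary entry can be made on a day without a movement.

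**The wording of the four-day rule.** It refers to days of data observed, not days with a movement. Under Section 4.3.1 a compliant subject's day without a movement still carries a diary report and a dose record.

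**Rescue days.** Section 9.3.2 removes movements that fall within 24 hours of rescue. It does not declare the day missing.

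**The case for a change.** The best case for a change is that this is the primary endpoint and the text leaves room for two results. A dose record is not a CSBM assessment, which is what the formula names. The diary manual may govern data entry, but the derivation belongs in the analysis section. Simulated shifts can also be as large as the planned 10-point difference. With one common Poisson rate and baseline fixed at 0.5 CSBM a week, overall response falls from 14.6% to 3.8% (5 movements a week, 60% complete) and from 41% to 21% (6 a week, 60% complete).

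The ambiguity stands, and so does the conditional arithmetic. The size is less secure, because every figure presupposes the movement-day reading and depends on assumed rates. At 40% completeness the same model moves little: 0.3% to 0.3% at 5 a week and 2.0% to 2.9% at 6 a week. With gamma variation between subjects (shape 3) and 5 movements a week, response goes from 28.5% to 22.0% at 60% complete and from 9.6% to 10.7% at 40%. A lognormal model gives 16.8% to 5.8% (4 a week, 60%) and 19.7% to 13.3% (6 a week, 40%). Even the direction is not fixed.

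Nor can it be shown that the planning rates cease to apply, because the weekly computation in the cited study is not in the documents. The rule applies alike to both blinded arms, and no bias in the comparison has been demonstrated.

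**Conclusion.** Section 9.3.2 leaves an observed day undefined. That is missing detail rather than a rule that gives a wrong answer. Daily diary completion, daily dose records, the wording of the four-day rule and a compliance criterion that is hardly workable otherwise all lead to the same ordinary convention. A day with a completed diary and no movement is an observed zero. The same holds for a day whose only movement is disregarded for rescue, and for baseline. Under that convention, with all 7 days reported, the frequency equals the CSBM count and neither misclassification arises. Proration then acts only on days without a diary report, which is its purpose.

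This conclusion assumes that the diary, whose instructions are in the separate manual, can show that a day was completed without a movement. The protocol does not state this, but its compliance criterion is hard to apply otherwise. The size and direction of any effect on the treatment difference cannot be determined from the documents. Analysts would normally settle the convention in the derivation specification before unblinding; the plan itself need not change.

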4.2.1. Randomization

Subjects that meet the BM and Diary Compliance Criteria will be randomized using an automated interactive web response system (IWRS). The randomization schedule will be implemented in the automated interactive web response (IWR) system prior to kit distribution to the site. At the time of randomization the IWRS will assign a drug kit number for site personnel to dispense to the subject. Subjects will be stratified into one of the following two groups:

Group 1: Subjects < 65 years of age at time of randomization Group 2: Subjects ≥ 65 years of age at time of randomization

The site personnel must only dispense a drug kit that has been assigned by the IWRS. Dispensing kits out of order is considered a protocol violation.

Vital signs will be taken. Subjects will be queried for any adverse events or changes to their concomitant medications.

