9.4. Study Populations

The following populations have been defined for data analyses.

9.4.1.Intention-to-Treat (ITT) Population

This population includes all subjects randomized to treatment and will be used for sensitivity analysis of the primary efficacy endpoint.

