9.4.3. Per-Protocol Population

The per protocol (PP) population will consist of all subjects in the mITT population who have not violated the study eligibility criteria and have not deviated significantly from the protocol during the course of the study. Any efficacy analyses from this population will be considered as supportive to the ITT and mITT analyses. Reasons for exclusion from the PP population will be defined prospectively in the statistical analysis plan and prior to unblinding of the data.

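### Randomization is stratified by age group, but the primary CMH test controls only for study center and the supplied text gives no age-adjusted analysis of the primary endpoint (minor mismatch)

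*Combined protocol and SAP*

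**What the plan says.** Section 4.2.1 (Randomization) names one stratification factor, age at randomization: "Subjects will be stratified into one of the following two groups". The groups are under 65 and "Subjects ≥ 65 years of age at time of randomization". Center is not named as a factor, and the section does not say whether allocation was also blocked by site.

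Section 9.3.2 gives the primary test: "The primary efficacy endpoint will be analyzed using the CMH test controlling for the effect of study center". On small centers it adds: "The strategy for pooling centers will be based on geographical considerations, with low enrolling centers pooled by geographic region". It sets no size threshold, number of regions or target number of pooled centers, but says that any pooling will be documented before database lock and unblinding. The only interaction check is treatment by center.

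Age appears elsewhere in four places:
- Section 9.3.1 lists it for baseline comparison: "An analysis of baseline comparability of the following demographic and baseline characteristics for the treatment groups will be performed".
- The secondary endpoints in section 9.3.2 include "Overall response by gender and age group", with no method stated.
- Section 9.3.3 allows optional safety summaries by age.
- Section 3.2 plans for about 30% elderly subjects.

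For the ITT population, section 9.4.1 says: "This population includes all subjects randomized to treatment and will be used for sensitivity analysis of the primary efficacy endpoint". That analysis changes the population and says nothing about the adjustment. The per-protocol analysis in section 9.4.3 is likewise a change of population. Section 9.4.3 also points to further text: "Reasons for exclusion from the PP population will be defined prospectively in the statistical analysis plan". No separate SAP text with detailed methods is in the supplied document.

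**The concern.** A trial that stratifies allocation by a factor would normally use that factor in its primary test or say why not. This plan does neither. If age predicts response, stratified allocation makes the arms more alike on age than chance would. A test that ignores age then uses a variance that is slightly too large. The possible consequences are a type I error below the nominal 5%, some effect on power, and an age-adjusted analysis that would be post hoc if it were added after unblinding.

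**Working it through.** **1. The plan's own figure.** Section 9.1 gives 300 per arm, 20% versus 10%, two-sided 0.05 and about 90% power. The mean rate is 0.15.
- Null SE = √(2 × 0.15 × 0.85 / 300) = 0.02915.
- Alternative SE = √((0.2 × 0.8 + 0.1 × 0.9) / 300) = 0.02887.
- Uncorrected power = Φ((0.10 − 1.96 × 0.02915) / 0.02887) = Φ(1.485) = 93.1%.
- With a continuity correction of 1/300, power = Φ(1.369) = 91.5%. Fisher's exact test gives 92.0%.

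The stated figure is reproduced approximately and is slightly cautious.

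**2. Size of the conservatism, by hand.** The documents give no age effect, so one is assumed: placebo response 7% under 65 and 17% at 65 or over (odds ratio 2.7), with 30% older.
- Overall rate = 0.7 × 0.07 + 0.3 × 0.17 = 0.10. Total variance = 0.10 × 0.90 = 0.090.
- Variance due to age = 0.7 × 0.3 × (0.17 − 0.07)² = 0.0021.
- Share left after age = 1 − 0.0021 / 0.090 = 0.977. Its square root is 0.988.
- Type I error when age is balanced by design but ignored in the test ≈ 2Φ(−1.96 / 0.988) = 2Φ(−1.983) = 4.7%.

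With a milder effect (8.5% and 13.5%) the same steps give 0.7 × 0.3 × 0.05² = 0.000525, a remaining share of 0.994, and 4.9%.

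**3. Type I error by simulation.** The number of centers, center effect, age effect and block size are not in the documents. The runs assumed 600 subjects, 30% older, blocks of 4 and no dropout. CMH was used without continuity correction.

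| Setting | Center only | Age added |
|---|---|---|
| Age odds ratio 3, mean of 12 scenarios, no site blocking | 4.71% | 5.10% (age × pooled center) |
| Same, with site blocking | 4.76% | 4.94% (age × pooled center) |
| 30 equal centers, placebo 7% / 17%, 40,000 runs | 4.5% | 4.7% (age × center) |
| 30 equal centers, placebo 8.5% / 13.5%, 40,000 runs | 5.0% | 5.0% (age × center) |

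At age odds ratio 1 the center-only mean is 5.02% without site blocking and 4.94% with it. The Monte Carlo SE of a 12-scenario mean is about 0.08 points. The simulations agree with the hand calculation.

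**4. Power of the planned test.** Center-only CMH was run at 20% versus 10% with 10, 20, 40 or 60 uneven centers, center SD 0, 0.5 or 1 on the logit scale, and age odds ratio 1, 2 or 3. Power is 90.8-94.7% without site blocking and 92.6-95.6% with it. All 72 scenarios are above 90%. There were 6,000 trials per scenario, with an SE of about 0.3 points.

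**5. Change in power when age is added (points).**

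| Centers | No site blocking | Site blocking |
|---|---|---|
| About 5 to 12 pooled | −0.5 to +0.5 | −0.2 to +0.5 |
| 12 equal | −0.5 to 0.0 | −0.1 to +0.4 |
| 25 equal | −1.37 to −0.45 | −0.3 to +0.5 |
| 40 unpooled | −2.0 to −1.2 | −0.7 to +0.2 |
| 60 unpooled | −3.3 to −1.9 | −1.1 to −0.4 |

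The lowest power with age crossed with unpooled centers is 87.8% without site blocking and 91.9% with it. A separate run without site blocking lost 0.5 to 2.2 points at 30 equal centers. The pooled row rests on an assumed rule: centers with fewer than 30 subjects merged into 4 regions.

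**6. Why the number of centers matters.** Older subjects number about 0.30 × 600 = 180, and the mean response is 15%. Twelve pooled centers give 180 / 12 = 15 older subjects and 15 × 0.15 = 2.25 expected responders per older stratum. Sixty centers give 3 subjects and 0.45 responders. A stratum with no responders, or with only one arm, adds nothing to the CMH statistic.

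**The case against.** The strongest reply is that the plan breaks no rule of its own: nothing in it promises that the stratification factor will enter the analysis. The planned test is valid, slight conservatism can hurt only the sponsor, and adding age brings no demonstrated gain in power. With many unpooled centers and no site blocking it can take power below the stated 90%. All of this stands, and it is why the point is minor.

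It is also true that the half-point cost depends on a pooling rule that section 9.3.2 does not state. Holding pooled centers to about a dozen may mean merging centers that the plan would keep separate, which coarsens the center adjustment and is a further change to the primary analysis. This also stands and belongs in the cost.

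A third reply is that age is already covered by the secondary listing of response by age group. That shows age is not ignored, but a subgroup breakdown does not adjust the overall comparison.

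A reader might also infer that controlling for center is itself an error because center is not a named stratum. The text does not support that. Adjusting for center is legitimate, and if allocation was also blocked by site, the center term reflects the randomization and only age is left out.

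**Conclusion.** The mismatch is real and minor. Age group drives the allocation, the primary test does not use it, and the supplied text gives neither a reason nor an age-adjusted analysis of the primary endpoint. Type I error is about 4.5-4.9% if age is strongly prognostic and about 5% if it is not. Power stays above 90% in every scenario run for the planned test.

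Two stronger readings should be resisted. One is that leaving age out invalidates the primary test, inflates its type I error or underpowers the trial; the calculations show none of these. The other is that the sponsor has planned no age-adjusted analysis at all. Section 9.4.3 refers to a statistical analysis plan whose detailed methods are not in the supplied text, so the finding covers only what is supplied.

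That age is left out of the primary test follows from the text alone. The sizes rest on assumed center numbers, center and age effects, block size and pooling, shown as ranges under both allocation schemes.

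**What to change.** Before unblinding, state in section 9.3.2 that the primary endpoint will be analyzed by a CMH test stratified by the randomization age group, as defined in section 4.2.1, crossed with pooled center. Fix the pooling rule in the same edit, so that the crossed strata are not sparse. Keep the center-only CMH as a sensitivity analysis.

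If pooling as planned would leave many centers (about 25 or more), keep the center-only CMH as primary and prespecify the age-stratified CMH as a sensitivity analysis, with a line saying why the primary test omits the stratum. If the SAP already specifies an age-adjusted analysis, a cross-reference is enough.

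No new data are needed, because the IWRS already holds the age group. The text change is a few sentences. Adding age to the primary test costs about half a point of power or less with a dozen or fewer pooled centers, plus possibly a coarser center adjustment. Crossing age with many unpooled centers costs about 1 to 3 points if allocation was not blocked by site, and less if it was. The sensitivity-analysis option leaves the primary test untouched.
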